4.12	Distance Over-Refraction and Distance Visual Acuity	Perform a distance over-refraction OD and OS using loose lenses outside of the phoropter under ambient room illumination. The distance over-refraction may also be refined under binocular conditions. Record the results. The results of the distance over-refraction may also be checked for the impact on near vision under monocular and/or binocular conditions.	
4.13	Subjective Lens Fit Assessment	
Evaluate overall lens fit acceptance (acceptable or unacceptable) based on centration, movement and other fitting characteristics.
 
An unacceptable fit is deemed by one of the following criteria:
 
 • limbal exposure at primary gaze or with extreme eye movement; • edge lift; • excessive movement in primary and up gaze; or 	[REDACTED]

		
 insufficient movement in all three of the following conditions: primary gaze, up gaze, and Josephson push up. 
If either lens is deemed unacceptable, the subject will be discontinued from the study. Remove the lenses, perform a slit-lamp evaluation, and complete the Final Evaluation form.
	
4.14	Modifications	
If the subject reports unsatisfactory vision or is unable to obtain 20/30 distance visual acuity OU with the lenses, then a modification must be attempted. If the subject reports satisfactory vision with the lenses a modification is not required, however at the Investigator's discretion and based upon their findings on the measured visual acuity and/or over- refraction the investigator may make a modification.
 
Up to two attempts at modification are permitted if necessary, in order to achieve an acceptable distance and near binocular performance for the subject, and to enable them to wear that particular lens type. Follow the fitting guide allowing for at least 10 minutes of settling time between each lens modification attempted.
 
If modifications are required steps 4.7-4.13 will be repeated for each modification.
	Appendix G or H (Fitting Guides)
4.15			
4.16	Distance and Near Exit Visual Acuity	
Distance and near Snellen visual acuity will be measured for each eye with the study contact lenses in place.
 
For near measures use the ETDRS 2000 Series Chart 1 or 2. The acuity will be recorded to the nearest letter OD, OS and OU.
 
NOTE: The distance visual acuity must be at least 20/30 OU for the lenses to be dispensed.
	
4.17	Dispensing Criteria	
The lenses will be dispensed for 3 ± 1 day.
 
 Distance Snellen acuity equal to or better than 20/30 OU. 	

		
 • Subject must indicate that the vision is acceptable. • Subject must indicate that the comfort of the lenses is acceptable. • Lenses must have an acceptable general lens fit. 	
4.18	Patient Instructions (Daily Reusable Lenses)	
Instruct the Subject the following:
 
 • The lenses will be worn on a daily wear reusable basis. • No additional lenses will be dispensed. • OPTI-FREE® PureMoist® disinfecting solutions will be used to rub, rinse and store the lenses each day. • If determined necessary by the Investigator sterile non-preserved rewetting drops may be dispensed to be used as needed for dryness. • Subjects will be instructed to wear lenses for a minimum of 6 hours a day, every day during the study. • Subjects will be instructed to wear their glasses when not wearing the study lenses. • Subjects will be instructed to bring their habitual contacts or spectacles to the next visit. • A patient instruction booklet will be provided. 
NOTE: In the event a lens is lost or damaged, the subject will return to the investigator site for replacement. As much as reasonably possible, a damaged lens should be returned to the investigational site and then returned to the Sponsor. If lens damage is present, complete the Product Quality Complaint Form. The lens will be stored in labeled vial with sterile saline and returned to the Sponsor.
	
4.19	Patient Instructions (Daily Disposable Lenses)	
Instruct the Subject the following:
 
 • The lenses will be worn on a daily wear basis. 	

		
 Only enough lenses will be dispensed to the subject to wear for the required number of days until their follow-up visit. No additional lenses will be dispensed. A new lens will be opened and worn each day. Instruct the subject to bring back all unworn study lenses. Instruct the subject no cleaning or disinfecting solutions will be used for this lens type. If determined necessary by the Investigator sterile non-preserved rewetting drops may be dispensed to be used as needed for dryness. Subjects will be instructed to wear lenses for a minimum of 6 hours a day, every day during the study. Subjects will be instructed to wear their glasses when not wearing the study lenses. A patient instruction booklet will be provided. 
NOTE: In the event a lens is lost or damaged, the subject will return to the investigator site for replacement. As much as reasonably possible, a damaged lens should be returned to the investigational site and then returned to the Sponsor. If lens damage is present, complete the Product Quality Complaint Form. The lens will be stored in labeled vial with sterile saline and returned to the Sponsor.
	
4.20	Schedule Follow-up	
The subject will be scheduled to return for their follow-up appointment in 3±1 day.
 
NOTE: To count the follow-up visit as a day of wear the Subject must have worn the study lenses for 6 hours prior to the visit.
	

VISIT 5

The subjects must present to Visit 5 wearing the study lenses. To be counted as a day of wear the lenses need to have been worn for at least six (6) hours prior to the visit.

Visit 5: Treatment 2 Follow-up 1		
Step	Procedure	Details
5.1	Adverse Events and Concomitant Medications Review	Review the subject's concomitant medications and record any changes from the previous study visit. Record any adverse events or medical history changes from the previous study visit.
5.2	Wear time and Comfortable Wear time with Study lenses Wear Time	Record the hours the subject has worn the study lenses and the comfortable wear time on the day of follow-up.
5.3	Compliance	Record the subject's compliance with wearing the study lenses. NOTE: Subjects must have worn lenses for at least 6 hours per day To be counted as a day of wear at this visit the Subject must have worn the study lenses for 6 hours prior to the visit.
5.4		
5.5	Ocular Symptoms	Subjects will respond to a verbal open-ended symptoms questionnaire.
5.6	Subjective Acceptance	Record whether the subject's distance and near vision with the lenses is acceptable.
5.7	Distance and Near Entrance Visual Acuity	Measure the distance and near visual acuity OD, OS and OU. Record the results. NOTE: Use the ETDRS 2000 Series Chart 1 or 2 near card placed at 40 cm to measure the Near visual acuity
5.8	Distance Over-Refraction and Distance Visual Acuity	Perform a distance over-refraction OD and OS using loose lenses outside of the phoropter under ambient room illumination. The distance over-refraction may also be refined under binocular conditions. Record the results and distance visual acuity OD and OS. The results of the distance over-refraction may also be checked for the impact on near vision under monocular and/or binocular conditions.

5.9	Determination of Lens Optimization	
If the subject reports unsatisfactory vision or is unable to obtain 20/30 distance visual acuity OU with the lenses, then a modification must be attempted.
 
If the subject reports satisfactory vision with the lenses a modification is not required, however at the Investigator's discretion and based upon their findings on the measured visual acuity and/or over-refraction the investigator may make a modification.
 
Up to two attempts at modification are permitted if necessary, in order to achieve an acceptable distance and near binocular performance for the subject, and to enable them to wear that particular lens type.
 
Follow the fitting guide and steps 4.7-4.13 in Visit 4 Fitting allowing for at least 10 minutes of settling time between each lens modification.
	Appendix G or H (Fitting Guides)
5.10	Lens Fit Assessment:	
Evaluate and grade lens centration, primary gaze movement, upgaze movement and tightness (push-up test).
 
 • The subject should not proceed to wear the lenses if any of the following is observed: • presence of limbal exposure (appearance of clear cornea) in any gaze • presence of edge lift • presence of unacceptable movement (excessive or insufficient) in all three movement categories (primary gaze, upgaze, and push-up). 
If either lens is deemed unacceptable, the subject will be discontinued from the study. Remove the lenses, perform a slit-lamp evaluation, and complete the Final Evaluation form.
	
5.11	Collection of unworn lenses (if applicable)	
If the subject was fit in the daily disposable lenses at visit 4 collect unworn lenses returned by the subject when lens power has been optimized.
	

		If lens power was not changed allow the subject to use the unworn lenses dispensed at Visit 4 and dispense enough lenses of the same power to last the subject until their next visit.	
5.12	Lens Removal	The study lenses will be removed and discarded.	
5.13	Biomicroscopy	
Perform biomicroscopy OD and OS. Slit Lamp Classification Scales will be used to grade the findings.
 
For the conjunctival redness [REDACTED] 0.5 unit increments will be used in the grading.
 
Corneal Staining Assessment [REDACTED] will be graded in 1.0 increments.
 
If the clearance of the fluorescein needs to be expedited, preservative-free rewetting drops may be instilled.
	[REDACTED] [REDACTED] [REDACTED]
5.14	Insertion of Study Lenses	Dispense the subject a new pair of lenses that match the distance and ADD power of the lenses that were removed in Step 5.12 above.	
5.15	[REDACTED]	[REDACTED]	
5.16	Distance and Near Exit Visual Acuity	
Distance and near Snellen visual acuity will be measured for each eye with the study contact lenses in place.
 
For near measures use the ETDRS 2000 Series Chart 1 or 2. The acuity will be recorded to the nearest letter OD, OS and OU.
 
NOTE: The distance visual acuity must be at least 20/30 OU for the lenses to be dispensed.
	[REDACTED]
5.17	Dispensing Criteria	
The lenses will be dispensed for 7±1 day.
 
 • Distance Snellen acuity equal to or better than 20/30 OU • Subject must indicate that the vision is acceptable. • Subject must indicate that the comfort of the lenses is acceptable. • Lenses must have an acceptable general lens fit. 	

5.18	Patient Instructions (Reusable Lenses)	
Instruct the Subject the following:
 
 • The lenses will be worn on a daily wear reusable basis. • No additional lenses will be dispensed. • OPTI-FREE® PureMoist® disinfecting solutions will be used to rub, rinse and store the lenses each day. • If determined necessary by the Investigator sterile non-preserved rewetting drops may be dispensed to be used as needed for dryness. • Subjects will be instructed to wear lenses for a minimum of 6 hours a day, every day during the study. • Subjects will be instructed to wear their glasses when not wearing the study lenses. • Subjects will be instructed to bring their habitual contacts or spectacles to the next visit. 
NOTE: In the event a lens is lost or damaged, the subject will return to the investigator site for replacement. As much as reasonably possible, a damaged lens should be returned to the investigational site and then returned to the Sponsor. If lens damage is present, complete the Product Quality Complaint Form. The lens will be stored in labeled vial with sterile saline and returned to the Sponsor.
	
5.19	Patient Instructions (Daily Disposable Lenses)	
Instruct the Subject the following:
 
 • The lenses will be worn on a daily wear basis. • Only enough lenses will be dispensed to the subject to wear for the required number of days until their follow-up visit. No additional lenses will be dispensed. • A new lens will be opened and worn each day. • Instruct the subject to bring back all unworn study lenses. 	

		
 • Instruct the subject no cleaning or disinfecting solutions will be used for this lens type. • If determined necessary by the Investigator sterile non-preserved rewetting drops may be dispensed to be used as needed for dryness. • Subjects will be instructed to wear lenses for a minimum of 6 hours a day, every day during the study. • Subjects will be instructed to wear their glasses when not wearing the study lenses. • Subjects will be instructed to bring their habitual contacts or spectacles to the next visit. 
NOTE: In the event a lens is lost or damaged, the subject will return to the investigator site for replacement. As much as reasonably possible, a damaged lens should be returned to the investigational site and then returned to the Sponsor. If lens damage is present, complete the Product Quality Complaint Form. The lens will be stored in labeled vial with sterile saline and returned to the Sponsor.
	
5.20	Schedule Follow-up	
The subject will be scheduled to return for their follow-up appointment in 7 ± 1 day.
 
NOTE: To count the follow-up visit as a day of wear the Subject must have worn the study lenses for 6 hours prior to the visit.
	

VISIT 6

The subjects must present to Visit 6 wearing the study lenses. To be counted as a day of wear the lenses need to have been worn for at least six (6) hours prior to the visit.

Visit 6: Treatment 2 Follow-up 2			
Step	Procedure	Details	
6.1	Adverse Events and Concomitant Medications Review	Review the subject's concomitant medications and record any changes from the previous study visit.	

		Record any adverse events or medical history changes from the previous study visit.	
6.2	Wear time and Comfortable Wear time with Study lenses	Record the hours the subject has worn the study lenses and the comfortable wear time on the day of follow-up.	
6.3	Compliance	Record the subject's compliance with wearing the study lenses. NOTE: Subjects must have worn lenses for at least 6 hours per day To be counted as a day of wear at this visit the Subject must have worn the study lenses for 6 hours prior to the visit.	
6.4	[REDACTED]	[REDACTED]	
6.5	Ocular Symptoms	Subjects will respond to a verbal open-ended symptoms questionnaire	[REDACTED]
6.6	Subjective Acceptance	Record whether the subject's distance and near vision with the lenses is acceptable.	
6.7	Distance and Near Entrance Visual Acuity	Distance and near Snellen visual acuity will be measured for each eye with the study contact lenses in place. For near measures use the ETDRS 2000 Series Chart 1 or 2. The acuity will be recorded to the nearest letter OD, OS and OU.	[REDACTED]
6.8	Visual Performance Distance (4 M) Intermediate (64 cm) Near (40 cm)	Visual performance will be recorded OD, OS, and OU for the following: Distance, Bright Illuminance High and Low Contrast ETDRS Charts 4 M- HC#1, HC#2, HC#3 and LC#1, LC#2, LC#3 Near, Bright Illuminance Reduced Guillou-Poling Charts Intermediate (64 cm) High Contrast and Low Contrast Near (40 cm) High Contrast and Low Contrast Distance, Dim Illuminance (with Distance goggles) High Contrast ETDRS Charts 4 M-HC#4, HC#5, HC#6	[REDACTED] [REDACTED] [REDACTED]

		
Near, Dim Illuminance (with Near goggles) Reduced Guillon-Poling charts High Contrast Intermediate (64 cm) and Near (40 cm).
 
NOTE:
 
 • The room illuminance must be between 7.3 and 7.9 EV (394-597 lux). • Distance, HC-1 Chart luminance Acceptable Range 10.5-10.7 EV (181-208 cd/m²). • Guillon-Poling, Near Chart Luminance Acceptable Range 10.8-11.1 EV (223-274 cd/m²). • Do not use the Mesopic filter for Dim luminance (Dim luminance will be simulated by using the goggles) 	
6.9	Binocular Distance Over-refraction and Distance Visual Acuity	
Perform a binocular over-refraction and record the OD and OS results and distance visual acuity.
 
Note: No lens changes are allowed based on the over-refraction.
	Appendix D
6.10	Lens Fit Assessment:	
Evaluate and grade lens centration, primary gaze movement, upgaze movement and tightness (push-up test).
 
The subject should not proceed to wear the lenses if any of the following is observed:
 
 • presence of limbal exposure (appearance of clear cornea) in any gaze • presence of edge lift • presence of unacceptable movement (excessive or insufficient) in all three movement categories (primary gaze, upgaze, and push-up). 
If either lens is deemed unacceptable, the subject will be discontinued from the study. Remove the lenses, perform a slit-lamp evaluation, and complete the Final Evaluation form.
	

6.11	Collection of unworn lenses (if applicable)	If the second lens type fit on the subject was the daily disposable lenses collect unworn lenses returned by the subject.	
6.12	Lens Removal	Have the subject remove the study lenses and store in saline in a labeled glass vial. NOTE: Lenses do not need to be stored in a refrigerator.	
6.13	Biomicroscopy	Perform biomicroscopy OD and OS. Slit Lamp Classification Scales will be used to grade the findings. For the conjunctival redness [REDACTED] 0.5 unit increments will be used in the grading. Corneal Staining Assessment [REDACTED] will be graded in 1.0 increments. If the clearance of the fluorescein needs to be expedited, preservative-free rewetting drops may be instilled.	[REDACTED] [REDACTED] [REDACTED]

FINAL EVALUATION

The final evaluation will ordinarily take place immediately following the last scheduled follow-up visit per the study protocol. It may also take place at any point the subject discontinues the study or is terminated from the study.

Final Evaluation			
Step	Procedure	Details	CTP
F.1	Final Exam Form	Indicate if the subject completed the study successfully. If subject discontinued from the study, indicate the reason.	
F.2	Subjective spherocylindrical Refraction	Perform bare-eye subjective spherocylindrical refraction with a phoropter and record the best corrected distance visual acuity to the nearest letter (OD, OS, and OU).	[REDACTED] [REDACTED]
F.3	Exit Slit Lamp Biomicroscopy	FDA Slit Lamp Classification Scale will be used to grade the findings and determine eligibility. If the clearance of the fluorescein needs to be expedited, preservative-free rewetting drops or saline may be instilled.	[REDACTED]

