1.24	Determine Visual Satisfaction	Determine if the subject’s vision is acceptable with the lenses. Allow the subject to look down a hallway or out of a window for distance vision assessments, and for them to read a book, magazine or similar for near vision.
1.25	Study Lens Distance and Near Visual Acuity	Measure the distance and near visual acuity OD, OS and OU. Record the results.

		NOTE: Use the ETDRS 2000 Series Chart 1 or 2 near card placed at 40 cm to measure the Near visual acuity	
1.26	Distance Over- Refraction and Distance Visual Acuity	
Perform a distance over-refraction OD and OS using loose lenses outside of the phoropter under ambient room illumination. The distance over-refraction may also be refined under binocular conditions. Record the results. The results of the distance over-refraction may also be checked for the impact on near vision under monocular and/or binocular conditions.
	
1.27	Subjective Lens Fit Assessment	
Evaluate and grade lens centration, primary gaze movement, upgaze movement and tightness (push-up test).
 
 • The subject should not proceed to wear the lenses if any of the following is observed: • presence of limbal exposure (appearance of clear cornea) in any gaze • presence of edge lift • presence of unacceptable movement (excessive or insufficient) in all three movement categories (primary gaze, upgaze, and push-up). 
If either lens is deemed unacceptable, the subject will be discontinued from the study. Remove the lenses, perform a slit-lamp evaluation, and complete the Final Evaluation form.
	
1.28	Modifications	
If the subject reports unsatisfactory vision or is unable to obtain 20/30 distance visual acuity OU with the lenses, then a modification must be attempted. If the subject reports satisfactory vision with the lenses a modification is not required, however at the Investigator's discretion and based upon their findings on the measured visual acuity and/or over- refraction the investigator may make a modification. Up to two attempts at modification are permitted if necessary, in order to achieve an acceptable distance and near binocular performance for the subject, and to enable them to wear that particular lens type.
	

		Follow the fitting guide allowing for at least 10 minutes of settling time between each lens modification attempted. If modifications are required steps 1.21-1.27 will be repeated for each modification.	
1.29			

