2.3	Compliance	
Record the subject's compliance with wearing the study lenses.
 
NOTE: Subjects must have worn lenses for at least 6 hours per day To be counted as a day of wear at this visit the Subject must have worn the study lenses for 6 hours prior to the visit.
	
2.4			
2.5	Ocular Symptoms	Subjects will respond to a verbal open-ended symptoms questionnaire.	

2.6	Subjective Acceptance	Record whether the subject's distance and near vision with the lenses is acceptable.	
2.7	Distance and Near Entrance Visual Acuity	Measure the distance and near visual acuity OD, OS and OU. Record the results. NOTE: Use the ETDRS 2000 Series Chart 1 or 2 near card placed at 40 cm to measure the Near visual acuity	[REDACTED]
2.8	Distance Over-Refraction and Distance Visual Acuity	Perform a distance over-refraction OD and OS using loose lenses outside of the phoropter under ambient room illumination. The distance over-refraction may also be refined under binocular conditions. Record the results and distance visual acuity OD and OS. The results of the distance over-refraction may also be checked for the impact on near vision under monocular and/or binocular conditions.	
2.9	Determination of Lens Optimization	If the subject reports unsatisfactory vision or is unable to obtain 20/30 distance visual acuity OU with the lenses, then a modification must be attempted. If the subject reports satisfactory vision with the lenses a modification is not required, however at the Investigator's discretion and based upon their findings on the measured visual acuity and/or over- refraction the investigator may make a modification. Up to two attempts at modification are permitted if necessary, in order to achieve an acceptable distance and near binocular performance for the subject, and to enable them to wear that particular lens type. Follow the fitting guide and steps 1.21-1.27 in Visit 1 Fitting allowing for at least 10 minutes of settling time between each lens modification.	[REDACTED]
2.10	Lens Fit Assessment:	Evaluate and grade lens centration, primary gaze movement, upgaze movement and tightness (push-up test). 
 • The subject should not proceed to wear the lenses if any of the following is observed: • presence of limbal exposure (appearance of clear cornea) in any gaze • presence of edge lift 	[REDACTED]

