3.10	Lens Fit Assessment:	
Evaluate and grade lens centration, primary gaze movement, upgaze movement and tightness (push-up test).
 
 • The subject should not proceed to wear the lenses if any of the following is observed: • presence of limbal exposure (appearance of clear cornea) in any gaze • presence of edge lift • presence of unacceptable movement 	

		
(excessive or insufficient) in all three movement categories (primary gaze, upgaze, and push-up).
 
If either lens is deemed unacceptable, the subject will be discontinued from the study. Remove the lenses, perform a slit-lamp evaluation, and complete the Final Evaluation form.
	
3.11	Collection of unworn lenses (if applicable)	
If the first lens type fit on the subject was the daily disposable lenses collect unworn lenses returned by the subject.
	
3.12	Lens Removal	
Have the subject remove the study lenses and store in saline in a labeled glass vial.
 
Note: Lenses do not need to be stored in a refrigerator.
	
3.13	Biomicroscopy	
Perform biomicroscopy OD and OS. Slit Lamp Classification Scales will be used to grade the findings.
 
For the conjunctival redness [REDACTED] 0.5 unit increments will be used in the grading.
 
Corneal Staining Assessment [REDACTED] will be graded in 1.0 increments.
 
If the clearance of the fluorescein needs to be expedited, preservative-free rewetting drops or saline may be instilled.
	[REDACTED] [REDACTED] [REDACTED]
3.14	Distance and Near Exit Visual Acuity	
Distance and near Snellen visual acuity will be measured for each eye with the subject's habitual correction in place.
 
For near measures use the ETDRS 2000 Series Chart 1 or 2. The acuity will be recorded to the nearest letter OD, OS and OU.
	[REDACTED]
3.15	Schedule Follow-up	
The subject will be scheduled to return for their next appointment in 7 ± 3 days.
 
NOTE: Subject may wear their habitual spectacles or contact lenses during the washout period.
	

VISIT 4

The subjects may present to Visit 4 wearing their habitual spectacles or contact lenses, if required for their distance vision.

Visit 4: Baseline Treatment 2		
Step	Procedure	Details
4.1	Adverse Events and Concomitant Medications Review	
Review the subject's concomitant medications and record any changes from the previous study visit.
 
Record any adverse events or medical history changes from the previous study visit.

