14. STATISTICAL METHODS

14.1. General Considerations

All data summaries and statistical analyses will be performed using the Statistical Analysis System (SAS) software Version 9.4 (SAS Institute, Cary, NC). Throughout the analysis of data, the results for each subject/eye will be used when available for summarization and statistical analysis. Unscheduled visits will be summarized separately and will be excluded from the statistical analysis.

Summary tables (Descriptive statistics and/or frequency tables) will be provided for all baseline variables, efficacy variables and safety variables as appropriate. Continuous variables will be summarized with descriptive statistics (n, mean, standard deviation [SD], median, minimum and maximum). Frequency count and percentage of subjects or eyes within each category will be provided for categorical data.

Summaries will be presented by study lens type and will be performed separately by completion status (Safety Population or Per-Protocol Population). All analyses will be conducted on per-protocol population (see Section 14.3).

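### Step 4.13 states a different movement-failure rule for the second lens than step 1.27 does for the first, so per-protocol membership can depend on crossover period

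*Combined protocol and SAP*

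**What the plan says.** Section 7.2 (with 7.3 for unscheduled visits) contains seven fit-assessment steps. In six of them (1.27, 2.10, 3.10, 5.10, 6.10 and U.8) the movement item that bars further wear is "presence of unacceptable movement (excessive or insufficient) in" all three "movement categories (primary gaze, upgaze, and push-up").

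Step 4.13, the fitting of the second lens at Visit 4, is worded differently. It gives two movement grounds. One is "excessive movement in primary and up gaze; or"; the other is insufficient movement in primary gaze, upgaze and push-up together. The first has no push-up condition.

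The lead instruction differs too. Step 1.27 says "Evaluate and grade lens centration, primary gaze movement, upgaze movement and tightness (push-up test"), whereas step 4.13 says "Evaluate overall lens fit acceptance (acceptable or unacceptable) based on centration, movement and other fitting characteristics".

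All seven steps discontinue the subject if either lens is unacceptable. The modification steps (1.28, 4.14) are triggered by vision, acuity or over-refraction, so they give no stated route for rescuing a failed fit.

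Refits inherit the split. At Visit 2, step 2.9 says "Follow the fitting guide and steps 1.21-1.27 in Visit 1 Fitting"; at Visit 5, step 5.9 says "Follow the fitting guide and steps 4.7-4.13 in Visit 4 Fitting".

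On analysis, section 14.1 states "All analyses will be conducted on per-protocol population", and section 14.3 limits that population to subjects who completed every visit without substantial deviation.

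**The concern.** In a 2×2 crossover the two periods should be run alike, so that lens and period can be separated. Here the written rule for stopping a subject on lens movement changes between the first and second fitting. Step 4.13 is met only by the second lens, and which lens that is depends on the randomised sequence.

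Movement is also one of the two primary endpoints. A subject stopped at Visit 4 leaves the per-protocol set altogether, and the Visit 3 endpoint data already collected go too. Retention can therefore depend on the period and on a finding related to the endpoint. If one lens produced the affected grade patterns more often, exclusion would differ by sequence and the lens comparison could be distorted.

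**Working it through.** **1. The two rules.** The plan states no figure to reproduce. Grade each of primary gaze, upgaze and push-up as insufficient (I), acceptable (A) or excessive (E), and write a pattern in that order.

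- Common rule (1.27, 2.10, 3.10, 5.10, 6.10, U.8): fail if none of the three is A, reading the words category by category.
- Step 4.13 rule: fail if primary gaze and upgaze are both E, whatever the push-up, or if all three are I.

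**2. Enumeration.** There are 3 × 3 × 3 = 27 patterns.

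| | Count | Patterns |
|---|---|---|
| Fail under common rule | 2 × 2 × 2 = 8 | every pattern without A |
| Fail under step 4.13 | 3 + 1 = 4 | E-E-E, E-E-A, E-E-I; I-I-I |
| Fail under both | 3 | E-E-E, E-E-I, I-I-I |
| Fail only at 4.13 | 4 − 3 = 1 | E-E-A |
| Fail only under common rule | 8 − 3 = 5 | I-I-E, I-E-I, I-E-E, E-I-I, E-I-E |

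Discordant patterns: 1 + 5 = 6 of 27. With a single rule at all steps the count is 0.

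The five patterns that go the other way all mix excessive with insufficient movement. If mixed patterns are set aside as unlikely, 8 + 8 − 1 = 15 remain (only A and E, or only A and I, with A-A-A counted once). The common rule then fails 2, step 4.13 fails 3, and the one discordant pattern is E-E-A.

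**3. Where it acts.** The operative contrast is 1.27 against 4.13. Through 2.9 and 5.9 the same contrast applies to refits, so a lens refitted at Visit 5 meets both rules (4.13 via 5.9, then 5.10). The endpoint visits, 3.10 and 6.10, share the common rule.

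**4. Route to the analysis.** Unacceptable at 4.13 → discontinued → visits not completed (14.3) → outside the only population analysed (14.1).

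**5. When the lens odds ratio is affected.** Let q be the share of subjects stopped at Visit 4 only because of the rule difference. The documents give no q, so it is an assumption. Take 25 subjects per sequence (half of the 50 enrolled), 0.75 optimal for both lenses (the control proportion in section 14.2), independence between lenses, and suppose every stopped subject would have been non-optimal.

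- Equal q, for example 2% for each lens: 25 × 0.98 = 24.5 remain per sequence. Each lens has proportion 0.75 when worn first and 0.75/0.98 = 0.765 when worn second, averaging 0.758. Both lenses give 0.758, so the odds ratio stays at 1.00.
- Unequal q: the two averages differ and the odds ratio moves in favour of the lens with the higher q. Its size depends wholly on values the documents do not supply, so none is given.

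**6. Separate minor item.** Table 3 heads Visit 5 as Day 3±1 in one panel and 3±3 in three; steps 4.17 and 4.20 say 3±1. Adding the 7±1 days to Visit 6:

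- 3±1: (2 to 4) + (6 to 8) = 8 to 12 days, matching sections 1.2 and 4.2.
- 3±3: (0 to 6) + (6 to 8) = 6 to 14 days, which does not match.

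**The case against.** Much can be said on the other side, and most of it limits the point rather than removing it.

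- **The common list is not stated to be exhaustive.** The dispensing criteria separately require the general fit to be acceptable, section 8.2 withdraws subjects for unacceptable fit, and both fitting guides (Appendices G and H) class excessive movement in primary or upward gaze as a loose fit. A reader might infer that a lens graded E-E-A would certainly be dispensed at Visit 1. The documents do not support that; a site could withhold it on these other grounds.
- **Step 4.13 might be read as simply stricter.** It is not: five patterns fail only under the other wording.
- **Bias in the lens comparison might be inferred.** Sequence is randomised, both lenses pass through 4.13, and period is in the model. The fitting guides give different movement figures for a well-fitted multifocal (0.1 to 0.5 mm for Test, 0.3 mm or less for Control), so a lens difference cannot be excluded. Nothing shows that the discordant patterns differ between lenses.
- **A percentage loss might be computed** by setting a lost subject's observations against those from 40 completers. That denominator is wrong. The lost subject is not a completer, about 50 − 40 = 10 subjects are allowed for, and sections 5.2 and 8.2 permit replacement. Losing the Visit 3 data follows from the completers-only population and applies to any late dropout.
- **Visit 4 failures might be thought impossible to reclassify,** because 4.13 asks for an overall judgement. This cannot be established: the lens-fitting procedure is redacted, and applying 4.13 already requires judging all three conditions.
- **Other relief.** The endpoint visits share one rule, section 14.2 calls the study a pilot, and section 14.9 plans multiple imputation if dropout exceeds 15%.

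What survives is that the printed rules conflict between periods and that each ends in discontinuation.

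**Conclusion.** The point holds as an internal conflict with a route into the analysis set. Step 4.13 and the other fit-assessment steps give different results for 6 of 27 grade patterns, one in one direction and five in the other. The difference falls between periods and carries into refits. Per-protocol membership can therefore depend on period through this wording alone.

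The size is limited to that count. It assumes that the common rule is read category by category and that the listed movement criteria are applied as printed; E-E-A is discordant even when mixed patterns are left out. How often any pattern occurs is unknown, so no bias size or loss percentage is claimed. The lens odds ratio is affected only if the discordant patterns are more common with one lens, and other text on fit may narrow the gap in practice. The Table 3 discrepancy is real but minor and unrelated to the fit rule.

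**What to change.** Reconcile step 4.13 with steps 1.27, 2.10, 3.10, 5.10, 6.10 and U.8 so that one fit-failure definition applies in both periods and in refits under 2.9 and 5.9. Which wording stands is for the sponsor's clinical team to decide. Add a table of fit-related discontinuations by lens and period, so that any imbalance is visible.

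Separately, reconcile the Visit 5 headers in Table 3 with steps 4.17 and 4.20 and with the stated 8-12 days of wear.

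The cost is protocol wording, matching eCRF text and one summary table. No extra procedures or visits are needed.
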